#### 8 STATISTICS AND DATA ANALYSIS

8.1 Sample size calculation

To replace colonoscopy and CTC the new testing strategy requires very high sensitivity to avoid false negative results and missed disease. False positive results are also undesirable, but these participants would simply follow the colonoscopy testing pathway that all participants follow currently. Therefore, the sample size calculations are based on achieving acceptable sensitivity. There are some data on the utility of FIT alone and urine VOC alone in the detection of SBD(6, 10, 37). Our recent study (n=562) is the only published study that evaluated the combination of both FIT and urine VOC for the detection of colon cancer, which was 97% (95% CI: 90 to 100), similar to that for colonoscopy(6). The sensitivity of FIT alone in detecting IBD is 0.85, with the combined accuracy of FIT and VOC unknown. On the basis of these previous studies, and the necessity for high sensitivity to replace colonoscopy, we assumed that the sensitivity (Se) of the FIT and urine VOC tests to detect SBD would be at least 0.97 which is very near 1.0. The confidence interval for such high sensitivity has to be adjusted such that the interval does not exceed 1.0. One recommended method is to use the Zhou-Li method as described in equations 4.5 to

replaced by Se. Assuming that the sensitivity of FIT and VOC to be at least 97% then for Se = 0.97 and a 95% CI width of 0.05 (ensuring a high precision around the sensitivity estimate) the required number of participants with SBD is 200. Further assuming that the prevalence of SBD in the population with bowel symptoms is 19% (likely underestimate), then 1053 participants are required. Based on previous study(6) about 55% of the participants would return both stool and urine samples and sufficient for FIT and VOC analyses. Thus, the total sample size required is 1,915.

This strategy is robust to changes in the underlying assumptions of test accuracy. Confidence intervals for sensitivity for different observed sensitivity for 150, 200 and 250 cases of SBD are shown in Figure 5(a). For the target sensitivity of 0.97, the width of the confidence interval is 0.05 with 200 SBD participants, with narrower and wider confidence interval limits, when the observed sensitivity is above and below this value, respectively (Figure 5(b)).

Figure 5 Confidence intervals for different estimates of sensitivity for 150, 200 and 250 cases of SBD.

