#### 8.2.2 Primary outcome analysis

The primary outcome is diagnostic accuracy - sensitivity, specificity, NPV and PPV of the dual index test, FIT and VOC. A FIT result that is >10 µgHb/g faeces OR a VOC result with predicted probability >0.63 implies that the participant is defined as having SBD and need to be referred for colonoscopy. We will report 2x2 tables of test accuracy of the dual test by the reference standard (final report from the CTC or colonoscopy examination and confirmatory histology report of SBD which is either colon cancer, colorectal adenomas or inflammatory bowel disease), alongside summary measures of sensitivity, specificity, NPV and PPV, and their 95% confidence intervals. Confidence intervals for sensitivity and specificity estimates that are very close to 1.0 will be according to the Zhou-Li method and the intervals for NPV and PPV estimates that are very close to 1.0 will be according to the Bayesian method (38). These test accuracy estimates will be used in the economic model.

We will analyse the combined FIT+VOC test results as both parallel (results from both tests are interpreted in combination) and serial testing (VOC performed only if FIT negative, i.e. <10  $\mu$ gHb/g faeces). The "or" rule will be considered in the interpretation of both parallel and serial tests where the diagnosis is positive when either test is positive (FIT >10  $\mu$ gHb/g faeces and/or VOC predicted probability >0.63), and negative when both are negative (FIT <10  $\mu$ gHb/g faeces and VOC predicted probability <0.63). In the serial test, if the FIT is positive (FIT >10  $\mu$ gHb/g faeces) then the diagnosis is positive. Otherwise, use the result from VOC and if it is positive (VOC predicted probability >0.63) then the diagnosis is positive. If the VOC result is also negative then the diagnosis is negative. Mathematically, both methods would give the same diagnostic results but would make a difference in the economic model.

A 2x2 table of test accuracy for each individual index test by the reference test will also be presented. Sensitivity, specificity, PPV and NPV will also be presented with their 95% confidence intervals for FIT only and VOC only. Participants with missing data for either of the index tests (FIT or VOC) or the reference standard (colonoscopy) will be excluded from this analysis.

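### The exclusion rule in 8.2.2 restricts FIT-only and serial accuracy to participants who also have VOC, which discards usable FIT results and leaves the FIT comparator open to a bias that cannot be sized from the protocol

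*Protocol*

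**What the plan says.** Section 8.2.2 of the protocol plans three sets of accuracy tables: the dual test read in parallel, the dual test read serially, and each index test alone.

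- The serial reading is described as "serial testing (VOC performed only if FIT negative"; a FIT above the cut-off settles the diagnosis as positive and VOC is consulted only otherwise.
- Parallel and serial readings are said to agree: "Mathematically, both methods would give the same diagnostic results but would make a difference in the economic model".
- Single-test accuracy "will also be presented with their 95% confidence intervals for FIT only and VOC only".
- The section then closes with the exclusion rule: "Participants with missing data for either of the index tests (FIT or VOC) or the reference standard (colonoscopy) will be excluded from this analysis".

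Section 8.1 plans on the basis that "about 55% of the participants would return both stool and urine samples and sufficient for FIT and VOC analyses". It does not divide the remaining 45% into stool only, urine only and neither.

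Sections 1.6 and 7.3 and note (b) to Table 1 let a triage FIT from the records serve as the study FIT when the procedure falls within four weeks of it. Section 1.6 adds that this first FIT decides how soon the procedure takes place, not whether it does.

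Section 8.2.3 plans sample return rates by SBD status and condition, a check of whether samples are missing at random, and missing-data sensitivity analyses without a named method. Return by FIT result is not listed.

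**The concern.** The exclusion rule asks for more data than two of the three analyses use. A participant with FIT and a reference result can be classified for FIT alone whatever happened to the urine sample. A FIT-positive participant also has a finished serial result. Removing both for want of VOC throws away information about FIT. The claimed equality of serial and parallel readings holds only where both results exist.

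FIT alone is the comparator for the study, and the gain from VOC is the quantity that would justify adding it. Section 8.2.2 also sends its accuracy estimates to the economic model, which compares FIT plus VOC with FIT (section 8.3). Fewer cases make the comparator less precise. If having a VOC result is related to the FIT result among people with SBD, complete-case FIT sensitivity is also biased, and so is the gain. The same argument applies to specificity among people without SBD.

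**Working it through.** **1. The plan's own figure.** 200 / 0.19 = 1052.6, rounded up to 1053; 1053 / 0.55 = 1914.5, rounded up to 1915. This matches section 8.1, so the total already assumes complete pairs. It leaves 1915 - 1053 = 862 participants outside the complete-case set.

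**2. Precision of FIT sensitivity.** Inputs: FIT sensitivity for SBD of 0.63, because section 1.9 (Dual Testing) reports 37% of SBD as FIT-negative; SBD cases enrolled = 1915 x 0.19 = 364. SE = sqrt(0.63 x 0.37 / n).

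- Complete pairs, n = 200: 0.034
- FIT available for 65% (assumption), n = 364 x 0.65 = 237: 0.031
- FIT available for 85% (assumption), n = 364 x 0.85 = 309: 0.027

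**3. Possible bias.** Let r+ and r- be the proportions with a usable VOC among FIT-positive and FIT-negative SBD cases that have FIT and reference results. Let v be the proportion of FIT-negative SBD that VOC detects; for the planned dual sensitivity of 0.97, v = (0.97 - 0.63) / 0.37 = 0.92.

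- Complete-case FIT sensitivity F = 0.63 r+ / (0.63 r+ + 0.37 r-)
- Dual sensitivity = 1 - (1 - F)(1 - v)
- Gain = (1 - F) v

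The return rates below are assumptions; the protocol gives none by FIT result. The last column is the share of SBD cases that would need a FIT for 55% to have both samples, namely 0.55 / (0.63 r+ + 0.37 r-).

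| r+ / r- | FIT | Dual | Gain | FIT availability implied |
|---|---|---|---|---|
| equal | 0.63 | 0.970 | 0.340 | depends on the common rate |
| 0.65 / 0.55 | 0.668 | 0.973 | 0.305 | 90% |
| 0.55 / 0.65 | 0.590 | 0.967 | 0.377 | 94% |
| 0.70 / 0.50 | 0.704 | 0.976 | 0.272 | 88% |
| 0.50 / 0.70 | 0.549 | 0.964 | 0.415 | 96% |
| 0.90 / 0.70 | 0.686 | 0.975 | 0.288 | 67% |
| 0.70 / 0.90 | 0.570 | 0.966 | 0.396 | 71% |

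FIT sensitivity and the gain each move by about 3 to 8 points and dual sensitivity by at most 0.7 point. The last two rows fit the 65 to 85% availability used in step 2; the other rows need more participants to have a FIT.

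Dual sensitivity is stable only because v is high. With v = 0.63 (the VOC sensitivity for cancer in Appendix D, borrowed as a low value), true dual sensitivity is 1 - 0.37 x 0.37 = 0.863, and the 0.50/0.70 and 0.70/0.50 pairs give 0.833 and 0.891.

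**4. The obvious patch fails.** Suppose FIT-positives without VOC are re-admitted and FIT-negatives without VOC stay out. With VOC available at random in 55% of both groups, FIT sensitivity becomes 0.63 / (0.63 + 0.37 x 0.55) = 0.756 and dual 1 - 0.244 x 0.08 = 0.980, against true values of 0.63 and 0.970.

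**The case against.** The strongest reply is that the serial rule says how results are read and the exclusion rule says who is analysed, so the two do not collide. All participants are asked for both samples, and complete pairs allow FIT and FIT plus VOC to be compared in the same people. That stands: complete pairs are a legitimate basis for the paired comparison and should be kept. It does not explain why FIT-only accuracy should also be limited to them. The word this in the exclusion sentence could refer only to the single-test tables just before it, but those include the FIT-only table, and the section gives no other rule for the dual test.

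A reader might infer that the FIT comparator will be biased, or that many of the 45% will have a FIT. The protocol supports neither. It gives no urine return by FIT result and no stool-only share, and section 1.6 says the proportion with a prior FIT cannot be estimated. Triage FIT sets procedure timing and could thereby shorten the time for giving urine, but urine is preferably collected at the clinic visit and has several fallback routes. If return is unrelated to FIT within disease status there is no bias, only lost precision. Even the sign is unknown.

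It is also fair that sections 8.2.1 and 8.2.3 plan comparisons of full and partial participants and missing-data sensitivity analyses, and that a statistical analysis plan may add detail. These do not alter the main rule, and the listed checks omit the relation to FIT on which the bias depends.

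**Conclusion.** The point holds in a limited form. The exclusion rule removes FIT results from analyses that do not need VOC. Where FIT exists without VOC the loss of precision is certain; its size, 0.034 against 0.027 to 0.031, assumes FIT for 65 to 85% of SBD cases. Bias in FIT sensitivity and in the gain is conditional on urine return depending on FIT within disease status. At assumed differences of 10 to 20 points it is about 3 to 8 points in either direction. Dual sensitivity, on which the study is sized, moves by less than 1 point if v is about 0.92, and more if VOC detects fewer FIT-negative cases.

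It would be tempting to conclude that the complete-case analysis should be replaced as the primary estimate. The protocol does not support going that far: the bias is undemonstrated and the paired comparison is sound on complete pairs. The gap is that the protocol does not secure an all-available FIT estimate or a named analysis resting on a weaker missing-data assumption.

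**What to change.** Amend section 8.2.2, or settle the following in the statistical analysis plan before the data are unblinded:

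1. Report the FIT-only table on everyone with FIT and reference results.
2. Keep the complete-pair tables, with the Zhou-Li interval where planned, for the paired comparison of FIT with FIT plus VOC.
3. Name as the missing-data analysis, separately in reference-positive and reference-negative participants: dual positivity = P(FIT+) + [1 - P(FIT+)] x P(VOC+ | FIT-). The first term uses everyone with FIT and reference results, and the last uses FIT-negatives with VOC and reference results. Give a bootstrap interval, and derive NPV and PPV using SBD prevalence in all participants with a reference result. This assumes that VOC is missing at random given FIT and disease status, which is weaker than the complete-case assumption but cannot be tested from the data.
4. Tabulate urine return by FIT result within SBD status.
5. State that FIT-positives lacking VOC are not re-admitted on their own.

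No new data are needed. The cost is wording, one extra bootstrap analysis, and FIT-only figures on two denominators, which the report must label clearly.

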#### 1.6 Impact of COVID-19 on Patient pathways

COVID-19 has brought about a change in the way people who are experiencing lower GI symptoms are referred into secondary care (illustrated in Appendix C Figure 3). Previously, FIT testing would be used in some regions, and only on low risk patients (~10% of all patients) before they were referred to secondary care. They would then be referred for colonoscopy only if the FIT test was positive. However, in most regions and patients, a person presenting to their GP with GI symptoms would be referred either routinely or urgently in accordance with the NICE guidelines (4) without the need for a prior FIT test.

Since the outbreak of COVID-19 within the UK, hospitals have seen a drastic fall in the number of patients being referred with GI symptoms. However since lockdown measures have eased and at time of writing this protocol, we are now beginning to see a rise in the number of referrals, and there is a backlog to be cleared. To manage limited colonoscopy capacity due to the impact of COVID-19 and colonoscopy (which is a potential aerosol generating procedure), FIT may be used (outwith) NICE guidance to triage referrals to colonoscopy.

In addition there has also been a stark increase in the number of patients being referred for a CT scan instead of colonoscopy. Our preliminary data shows that over 25% of all GI referrals to secondary are currently having CT scans. CT scan is a radiological procedure that was often favoured for older patients with comorbidities as they are more at risk of adverse events during a colonoscopy. However, COVID-19 has caused a shift in practice, whereby more people are now being referred for CT scans, and this shift appears to be here to stay for the long term. CT scans are split into regular CTs and CTC, the latter of which has been shown to have similar sensitivity to colonoscopy for the detection of colorectal cancer (Halligan et al., 2005) and large polyps (Pickhardt et al., 2003). It is common for CTC positive patients to then have a colonoscopy to receive histological confirmation of any diagnosis. Some NHS Trusts have already adopted CT scans for 100% of referrals, using colonoscopy as only a confirmatory diagnostic follow up.

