#### 1.8 Reference Standard

The reference standard will be complete colonoscopy or CTC.

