#### 7.5 Reference test

The reference test is the final report from the CTC or colonoscopy examination and confirmatory histology report. Biopsies are required as per national guidance (4) in the investigation of participants with lower gastrointestinal symptoms even in the absence of macroscopic abnormalities.

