#### 8.2 Statistical analysis

8.2.1 Summary of baseline data and flow of participants

The flow of participants through the study with outcome of the index tests (stool FIT and urine VOC) will be produced. The diagram will follow the template from STARD (Standards for Reporting of Diagnostic Accuracy Studies)(39). Descriptive statistics for the population will be presented in tables with comparisons made between those who do and do not consent to participate, and those who do and do not fully participate by providing a complete set of samples. Full details will be given for exclusions from analysis with reasons where available.

IRAS 282247\_RECEDE protocol\_v2.2\_11.02.2022 Page 27 of 50

Demographics and baseline characteristics will be summarised as mean and standard deviation, median and interquartile range (for continuous outcome) or frequency and percentage (for categorical outcome). The final diagnosis including histology where available from colonoscopy (the reference test) specifically diagnosis of SBD will be summarised as frequency and percentage.

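### Section 8.2.2 contradicts itself: its 2x2 table accepts CTC or colonoscopy as the reference standard, but its exclusion rule names colonoscopy alone

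*Protocol*

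**What the plan says.** The protocol defines the reference standard the same way in several places. Section 1.8: "The reference standard will be complete colonoscopy or CTC". Section 7.5: "The reference test is the final report from the CTC or colonoscopy examination and confirmatory histology report". The Study Summary, the Scientific Abstract (1.2) and section 8.2.3 agree. Section 8.2.2 does too where it sets up the primary 2x2 table, which it describes as follows: "final report from the CTC or colonoscopy examination and confirmatory histology report of SBD which is either colon cancer, colorectal adenomas or inflammatory bowel disease".

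Two places name colonoscopy alone:

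- The last sentence of 8.2.2, on who is left out of the analysis: participants with missing FIT or VOC "or the reference standard (colonoscopy) will be excluded from this analysis".
- Section 8.2.1, which summarises the final diagnosis "from colonoscopy (the reference test) specifically diagnosis of SBD".

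On what follows a CTC, section 1.6 says: "It is common for CTC positive patients to then have a colonoscopy to receive histological confirmation of any diagnosis". Section 6.6 gives CTC participants a check of their medical records. Later colonoscopy is recommended only to CTC-negatives who turn out FIT or VOC positive and have had no further specialist lower GI care.

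**The concern.** The sentence at issue is the only one in the protocol that says who is excluded from the accuracy analysis, and it disagrees with the definition used for the table in the same section.

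The two readings give different analysis sets. By the protocol's own account, whether a CTC participant also has a colonoscopy depends largely on the CTC result. If a missing colonoscopy means exclusion, CTC-negatives with no colonoscopy drop out while CTC-positives who were scoped stay in. Non-diseased participants are then lost selectively and prevalence in the analysed set rises.

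PPV and NPV are part of the primary outcome and depend directly on prevalence. Section 8.1 singles out NPV as of interest, and section 8.2.2 passes the accuracy estimates to the economic model.

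**Working it through.** **1. Reproduce the plan's figures (section 8.1).** 200 SBD cases at 19% prevalence: 200 / 0.19 = 1,052.6, so 1,053 analysable. With 55% returning usable samples: 1,053 / 0.55 = 1,914.5, so 1,915. Both match. The analysable set is therefore 200 SBD and 1,053 − 200 = 853 non-SBD.

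**2. Inputs the protocol does not give.**

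- *CTC share.* Section 1.6 says only: "Our preliminary data shows that over 25% of all GI referrals to secondary are currently having CT scans". It then splits CT into regular CT and CTC, so no CTC-specific share is available. I take 25% as the illustration and 50% to show the direction.
- *Specificity of the dual test.* None is stated. I take 0.3 to 0.8.
- *Simplifications.* Sensitivity is 0.97 (the section 8.1 target), CTC is perfect, every CTC-positive is scoped, and prevalence is the same in both modalities.

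**3. Analysed set under each reading.** Let f be the CTC share. The literal rule keeps 200 SBD and H = 853 × (1 − f) non-SBD.

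| Reading | Non-SBD dropped | Analysed | Prevalence |
|---|---|---|---|
| CTC or colonoscopy | 0 | 1,053 | 19.0% |
| Colonoscopy only, f = 25% | 853 × 0.25 ≈ 213 | ≈ 840 | 200 / 840 = 23.8% |
| Colonoscopy only, f = 50% | 853 × 0.50 ≈ 426 | ≈ 626 | 31.9% |

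**4. Predictive values.** True positives are 0.97 × 200 = 194 and false negatives 6.
PPV = 194 / (194 + (1 − Sp) × H); NPV = Sp × H / (Sp × H + 6).

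Worked at Sp = 0.5:

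- H = 853: PPV = 194 / (194 + 426.5) = 0.313; NPV = 426.5 / 432.5 = 0.986.
- H = 639.75 (f = 25%): PPV = 194 / (194 + 319.9) = 0.378; NPV = 319.9 / 325.9 = 0.982.

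| Sp | PPV, all kept | PPV, f = 25% | NPV, all kept | NPV, f = 25% |
|---|---|---|---|---|
| 0.3 | 0.245 | 0.302 | 0.977 | 0.970 |
| 0.5 | 0.313 | 0.378 | 0.986 | 0.982 |
| 0.8 | 0.532 | 0.603 | 0.991 | 0.988 |

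At f = 25%, PPV rises by about 0.06 to 0.07 and NPV falls by 0.003 to 0.007. At f = 50% and Sp = 0.5, PPV is 0.476 and NPV 0.973.

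**5. Sensitivity and specificity.** In this model selection depends on the CTC result and not on FIT or VOC. Sensitivity stays at 194 / 200 = 0.97, and specificity is the same fraction of a smaller H. Neither moves.

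**6. If not every CTC-positive is scoped.** At 80% scoped and f = 25%, SBD cases fall to 200 × 0.75 + 200 × 0.25 × 0.8 = 190. That costs some precision.

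**The case against.** The strongest reply is that the governing term is the reference standard, which the protocol repeatedly defines as CTC or colonoscopy. A participant with a CTC report is not missing it, and one parenthesis should not override those definitions. The protocol also recruits CTC participants, collects their results, follows them for at least 52 weeks (6.6) and plans to count disease missed by CTC (8.2.3). None of this fits a plan to discard CTC-negatives. Colonoscopy-only wording survives elsewhere too, for instance in the consent section (6.5), which points to incomplete editing. I accept this as the likely explanation. It does not settle what the rule says, because the conflict sits in the sentence that fixes the analysis set.

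The sentence might also be read as covering only the FIT-only and VOC-only tables just before it. That would not help: FIT alone is the comparator, and no other exclusion rule is given for the dual-test table.

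The STARD flow diagram and the itemised exclusions in 8.2.1 would make any large loss of CTC-negatives visible. They would not prevent it.

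Three stronger readings are tempting, and the protocol does not support them:

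- *Verification bias in sensitivity and specificity.* This needs selection that also depends on the index tests, or a different case mix by modality. If every CTC-negative with a positive FIT or VOC later had a colonoscopy that was counted, a true specificity of 0.50 would appear as (0.5 × 0.75) / (0.5 × 0.75 + 0.5) = 0.43 at a 25% share. But section 6.4 places those recommendations at the end of the study, and nothing says their results enter the primary table.
- *A deliberate choice to exclude CTC-negatives.* Nothing shows this intent.
- *Sites that would analyse almost only diseased participants.* Section 1.6 mentions Trusts using CT scans for all referrals, but not CTC specifically, and does not say that they are study sites.

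**Conclusion.** The point holds as an internal contradiction in a stated analysis rule. The exclusion sentence in 8.2.2 and the wording in 8.2.1 conflict with sections 1.8 and 7.5 and with the table definition in 8.2.2 itself. It is probably an editing remnant. Followed literally, it would tie inclusion to the reference result and shift the primary predictive values.

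The PPV shift in the 25% illustration is material; the NPV shift is small. Both sizes rest on the assumed CTC share, the assumed specificity range and the simplifications listed above, and should be read as illustrative. The target sensitivity and the planned 1,915 are not called into question. The correction is worth making before the analysis, because it removes the ambiguity at almost no cost.

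**What to change.** In 8.2.2, change the exclusion sentence so that it removes participants with *missing data for either index test (FIT or VOC) or for the reference standard (neither a complete colonoscopy nor a CTC report)*. In 8.2.1, write *colonoscopy or CTC (the reference test)*. Both then agree with sections 1.8 and 7.5, and the statistical analysis plan that section 8.2.3 announces should carry the same wording.

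The cost is a text correction in two places, with no change to sample size or data collection. The correction does not need a new rule on how CTC-negatives without histology are classified. Such a rule would have to take account of the record follow-up in section 6.6 and is a separate matter.
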